4.2. Per Protocol Analysis Set

4.2.1. Per Protocol Analysis Set in Stage 1

The Per Protocol Analysis Set in Stage 1 (PPAS1) is a subset of the FAS1 and includes subjects who did not have major protocol deviations. The list of major protocol deviations will be finalized by the project team prior to un-blinding of the study. The PPAS1 may be used in sensitivity analyses. For evaluation of sensitivity of the primary analysis in Stage 1 we will not use data collected after Week 12.

4.2.2. Per Protocol Analysis Set in Stage 2 and Amended Stage 2

The per protocol analysis set for pooled Stage 1, Stage 2, and Amended Stage 2, skin cohort (PPASS) is a subset of the PFASS and includes subjects who did not have major protocol deviations. The list of major protocol deviations will be finalized by the project team prior to un-blinding of the study. The PPASS may be used in sensitivity analyses. For evaluation of sensitivity of the primary analysis we will not use data collected after Week 12.

4.2.3. Per Protocol Analysis Set in Stage 3

The per protocol analysis set in Stage 3 (PPAS3) is a subset of the FAS3 and includes subjects who did not have major protocol deviations. The list of major protocol deviations will be finalized by the project team prior to un-blinding of the study. The PPAS3 may be used in sensitivity analyses. For evaluation of sensitivity of the secondary analysis in Stage 3 we will not use data collected after the participant receives 12 weeks of active treatment.

4.3. Safety Analysis Set

Multiple safety analysis sets are defined.

- The safety analysis set (SAS) includes all subjects who received at least one dose of randomized treatment in any stage.
- The safety analysis set in Stage 1 (SAS1) includes all subjects who received at least one dose of randomized treatment in Stage 1.
- The safety analysis set in Stage 2 (SAS2) includes all subjects who received at least one dose of randomized treatment in Stage 1 or Stage 2.
- The safety analysis set in Amended Stage 2 (SASA2) includes all subjects who received at least one dose of randomized treatment in Amended Stage 2.

• The safety analysis set in Stage 3 (SAS3) includes all subjects who received at least one dose of randomized treatment in Stage 3.

Subjects who are not treated will be excluded from the safety analysis.

- In Stage 1, the biomarker analysis population is defined as all enrolled subjects in Stage 1 who received at least one dose of PF-06823859 with at least one biomarker assessment.
- For Stage 1, Stage 2, and Amended Stage 2, the biomarker analysis population is defined as all enrolled participants in Stage 1, Stage 2 and Amended Stage 2 who received at least one dose of PF-06823859 with at least one biomarker assessment.
- In Stage 3, the biomarker analysis population is defined as all enrolled participants in Stage 3 who received at least one dose of PF-06823859 with at least one biomarker assessment.

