2.2. Study Design

Initially, this was a multi-center Phase 2A study planned to be conducted in approximately 30 adult participants with moderate to severe DM. Thirty two participants were randomized in order to collect data from 24 participants who completed the study. Each participant was to take part in the study for a period of approximately 9 months. After the 35 day screening period, participants who were eligible enrolled into the study and were randomized in a blinded manner, 2:1 (Active:Placebo) ratio. Investigational drug or placebo administration took place on Day 1, Week 4, and Week 8 of the study. Participants then entered a 5-month follow-up period.

For Stage 2, with the addition of 1 lower dose 150 mg arm, this study then became a Phase 2, dose-finding double-blind, randomized, placebo-controlled study. Approximately 20 additional participants who meet eligibility criteria will be enrolled and randomly assigned in a blinded manner to receive PF-06823859 600 mg, 150 mg, or placebo dosed every 4 weeks according to a randomization ratio. 5:11:4. Participants will receive study drug, (active or placebo) on Day 1, Week 4, and Week 8 of the study and when treatment is completed all participants will enter a 5-month follow-up period.

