- Absolute values and change from baseline in the values of selected biomarkers (Gene signature panel in blood and tissue; Human Myxovirus A (MXA), interferon gamma-induced protein 10 (IP-10), IFNbeta, high sensitive C-reactive protein, (hsCRP), muscle and bone blood biomarkers, autoantibody concentrations in serum/plasma) at all scheduled time points.
- Absolute values and change from baseline in the values of PROs (the short form (SF36) Health Survey, Dermatology and Life Quality Index (DLQI), 5D Itch Scale, and physician's evaluation of disease (PhGA)) at all scheduled time points. The brief description of the scales is presented in Section 9.4.
- Absolute values and change from baseline values of the sub-scores of CDASI activity and CDASI damage scores at all scheduled time points. The description on the scores is presented in Section 9.2.

3.2. Endpoints in Stage 2

3.2.1. Primary Endpoint in Stage 2

• Change from baseline in CDASI activity score at Week 12.

3.2.2. Secondary Endpoints in Stage 2

- Absolute values and change from baseline of CDASI activity and CDASI damage scores at all scheduled times points. (Exception: The change from baseline in CDASI activity score at Week 12 is a primary endpoint).
- Incidence of adverse events (AEs) laboratory abnormalities, changes in vital signs, and electrocardiogram (ECG) findings. The extended discussion of these endpoints is presented in Section 9.3.

CCI

- Absolute values and change from baseline in the values of selected biomarkers (Gene signature panel in blood and tissue; Human Myxovirus A (MXA), interferon gamma-induced protein 10 (IP-10), IFNbeta, high sensitive C-reactive protein, (hsCRP), muscle and bone blood biomarkers, autoantibody concentrations in serum/plasma) at all scheduled time points.
- Absolute values and change from baseline in the values of PROs (the short form (SF36) Health Survey, Dermatology and Life Quality Index (DLQI), 5D Itch Scale, and physician's evaluation of disease (PhGA)) at all scheduled time points. The brief description of the scales is presented in Section 9.4.
- Absolute values and change from baseline values of the sub-scores of CDASI activity and CDASI damage scores at all scheduled time points. The description on the scores is presented in Section 9.2.

3.3. Endpoints in Amended Stage 2

3.3.1. Primary Endpoint in Amended Stage 2

• Change from baseline in CDASI activity score at Week 12.

3.3.2. Secondary Endpoints in Amended Stage 2

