4. ANALYSIS SETS

4.1. Full Analysis Set

Multiple full analysis sets are defined. They are listed briefly here and described in more detail in Sections 4.1.1 through 4.1.2.

- The Full Analysis Set (FAS) includes all subjects who received at least one dose of randomized treatment in any study stage.
- The Full Analysis Set in Stage 1 (FAS1) includes all subjects who received at least one dose of randomized treatment in Stage 1.
- The Full Analysis Set in Stage 2 (FAS2) includes all subjects who received at least one dose of randomized treatment in Stage 2.
- The Full Analysis Set in Amended Stage 2 (FASA2) includes all subjects who received at least one dose of randomized treatment in Amended Stage 2.

- The Full Analysis Set in Stage 1 and Stage 2 (FAS12) includes all subjects who received at least one dose of randomized treatment in Stage 1 or Stage 2.
- The Pooled Full Analysis Set, skin cohort (PFASS) includes all subjects who received at least one dose of randomized treatment in Stage 1, Stage 2, or Amended Stage 2.
- The Full Analysis Set in Stage 3 (FAS3) includes all subjects who received at least one dose of randomized treatment in Stage 3.
- The Pooled Full Analysis Set, fixed sequence stages (PFASF) includes all subjects who received at least one dose of randomized treatment in Amended Stage 2 or Stage 3.

4.1.1. Full Analysis Sets in Stage 1, Stage 2, and Amended Stage 2

The FAS1 is defined as all subjects who have received at least one dose of randomized treatment in Stage 1. This is the primary analysis population for the safety and treatment compliance in Stage 1. In the analyses it is assumed that subjects are assigned to the randomized treatment regardless of what treatment was received. Note that Section 9.2 of the protocol references a modified intent to treat (mITT) set. In Stage 1, the mITT set in Stage 1 is synonymous with the FAS1 mentioned in this document.

The FAS2 is defined as all subjects who have received at least one dose of randomized treatment in Stage 2. This is the primary analysis population for the safety and treatment compliance in Stage 2.

The FAS12 is defined as all subjects who have received at least one dose of randomized treatment in Stage 1 or Stage 2. The FAS12 may be used for analyses assessing the durability of response for subjects in Stage 1 or Stage 2.

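### The SAP's biomarker populations require a dose of PF-06823859, which shuts out Stage 1 and original Stage 2 placebo participants and admits placebo-first participants only after the Week 12 switch

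*SAP*

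**What the plan says.** The three biomarker populations follow the safety sets in SAP 4.3 of the public text (a heading of their own may have been removed). Stage 1 uses "all enrolled subjects in Stage 1 who received at least one dose of PF-06823859 with at least one biomarker assessment". The pooled skin stages use "all enrolled participants in Stage 1, Stage 2 and Amended Stage 2 who received at least one dose of PF-06823859", again with at least one biomarker assessment. Stage 3 uses "all enrolled participants in Stage 3 who received at least one dose of PF-06823859 with at least one biomarker assessment".

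The neighbouring sets are worded differently. In SAP 4.1, "The Full Analysis Set in Stage 1 (FAS1) includes all subjects who received at least one dose of randomized treatment in Stage 1". In SAP 4.3, "The safety analysis set in Stage 1 (SAS1) includes all subjects who received at least one dose of randomized treatment in Stage 1". Both include placebo recipients.

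The biomarker endpoints in SAP 3 are "Absolute values and change from baseline in the values of selected biomarkers" at all scheduled visits. SAP 5.2 describes outcomes by visit and treatment group, and SAP 6.2.3 stratifies the pooled exploratory summaries by treatment group. The Schedules of Activities collect IP-10, MX-A and hsCRP from Day 1 with no restriction to active arms.

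**The concern.** An active-dose condition is natural for a pharmacokinetic set; Protocol 7.13 has placebo PK samples assayed only if a randomisation error is suspected. For a pharmacodynamic marker the placebo arm is what separates drug effect from time trend, background treatment and regression to the mean. A definition that removes it works against the stated aim of characterising the drug's pharmacodynamic effects and against reporting by treatment group.

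The second problem is selection. An active-first participant qualifies on Day 1. A placebo-first participant qualifies only on receiving active drug, scheduled from Week 12. On dosing days biomarkers are drawn before the infusion (Schedule of Activities footnotes for Amended Stage 2 and Stage 3), so the whole placebo-period record, including the Week 12 sample, exists before the event that decides whether it counts. That event can be related to outcome: under Protocol 5.8.6, a participant with a severe flare needing new or increased immunosuppression receives no further investigational product. A placebo-first participant who flares before Week 12 would leave the population; an active-first participant who does the same would stay.

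**Working it through.** **1. The definition against each stage's dosing (SAP 2.2).**

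- Stage 1: three infusions of active or placebo, then follow-up, with no switch. No placebo participant can qualify, short of a dosing error.
- Original Stage 2: participants who entered before Protocol Amendment 4 keep the parallel design. No placebo participant can qualify.
- Amended Stage 2 and Stage 3: placebo-first participants are due their first active dose at Week 12 and qualify only from then.

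**2. Stage 1 placebo count.** SAP 2.2 states that "Thirty two participants were randomized in order to collect data from 24 participants who completed the study" and that participants "were randomized in a blinded manner, 2:1 (Active:Placebo) ratio". Placebo = 32 × 1/3 = 10.7, about 11. Number qualifying: 0.

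**3. Pooled skin cohort.** SAP 2.2 gives about 20 further participants at 5:11:4 (600 mg : 150 mg : placebo). Placebo = 20 × 4/20 = 4. Total placebo = 10.7 + 4 = 14.7, about 15.

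The documents do not say how these 4 divide between original and Amended Stage 2, and they restate no ratio for Amended Stage 2. I assume that 5:11:4 covers both, so 0 to 4 are placebo-first.

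- All 4 placebo-first and all reach active drug: lost = (14.7 − 4)/14.7 = 73%.
- All 4 placebo-first, 80% reach active drug: kept = 3.2; lost = (14.7 − 3.2)/14.7 = 78%.
- None placebo-first: lost = 100%.

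The 80% is the Week 12 completeness assumption in Protocol 9.1.1. It is stated for Stage 1 only and is borrowed here.

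**4. Stage 3.** Protocol 9.1.3 plans 8 to 16 participants at 1:1, so 4 to 8 are placebo-first. At the same borrowed 80%, 3.2 to 6.4 would qualify.

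**5. What this does to precision, as an illustration.** The plan gives no precision figure for biomarkers, so I start from its CDASI figures in Protocol 9.1.2. Half-width of the 90% CI = 1.645 × SD × √(1/n₁ + 1/n₂).

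- 600 mg against placebo: 1.645 × 8 × √(1/21 + 1/11) = 4.90, as stated.
- 150 mg against placebo: 1.645 × 8 × √(1/10 + 1/11) = 5.75, as stated.

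In SD units, with 21 on 600 mg:

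| Placebo n | Half-width (SD) |
|---|---|
| 11 (plan's completers) | 0.61 |
| 4 (most that can qualify) | 0.90 |
| 3 (about 80% of 4) | 1.02 |

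In Stage 1 alone, placebo n = 0 and no contrast can be formed.

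**The case against.** The strongest reply is that the consequence cannot be read from the public text. The SAP sections between 6.1.3 and 6.1.3.3 are redacted, and no readable passage applies these populations to a named analysis. The analyses may run on the full analysis set; SAP 6.2.3 says only that the appropriate Stage 2 set is used. This stands. A reader might infer that the Stage 1 biomarker results will have no placebo arm. The documents support that only on the condition that this population governs.

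Three further limits also stand:

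- A reader might extend the point to the gene signature. SAP 6.1.3.3 sends the gene signature panel, muscle and bone markers and autoantibodies to a separate exploratory report, and Protocol 9.2.3.1 refers to an exploratory analysis plan. Neither is available, so their population is unknown.
- The endpoints are exploratory values and changes from baseline. No hypotheses are tested in the pooled or Stage 3 analyses, and the visible text specifies no biomarker contrast against placebo that would fail.
- A loss of about 11 of 15 is tempting as the pooled figure, but it is the minimum. It needs every Stage 2 placebo participant to be placebo-first and to go on to active drug.

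What does not stand is that the wording is harmless. If the analyses use this set, placebo is lost or selected. If they do not, the SAP carries a population that contradicts its own by-group reporting.

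**Conclusion.** The point holds as a defect in the definition, with a conditional consequence. Read literally, the rule excludes all of the roughly 11 Stage 1 placebo participants and about 73% to 100% of the roughly 15 in the pooled skin cohort. It also makes placebo-first inclusion in Amended Stage 2 and Stage 3 depend on reaching active drug. The counts rest on the stated allocation ratios being met and on 5:11:4 applying to about 20 participants across both forms of Stage 2.

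Wherever this population governs the IP-10, MXA and hsCRP summaries, Stage 1 has no comparator, and the remaining pooled and Stage 3 placebo participants are selected on an event after randomisation. The primary CDASI analysis and the stated sample-size figures do not depend on it. The change should be made because the rule as written defeats the use of placebo samples already scheduled, but it concerns exploratory endpoints only.

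**What to change.** In each of the three definitions, replace the requirement of a dose of PF-06823859 with a dose of randomized treatment, active or placebo, and keep the requirement of at least one biomarker assessment. State which analyses use the resulting sets. If an active-only set is wanted for exposure-response work, define and name it separately.

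The cost is SAP wording; no new samples or visits are needed. One caution applies to Stage 1. An internal committee separate from the blinded team reviewed unblinded data at the interim analysis in April 2020 (Protocol 1.6 and 9.5.1; SAP 7.1), and Protocol 9 allows summary-level Stage 1 data to be shared. The Stage 1 redefinition should therefore be dated and labelled as made after that interim analysis.

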5. GENERAL METHODOLOGY AND CONVENTIONS

5.1. Hypotheses and Decision Rules

5.1.1. Hypotheses and Decision Rules in Stage 1

The primary hypothesis to be tested is that there is no difference between the effects of treatment and placebo exposures on the CDASI activity score in Stage 1.

The primary endpoint in Stage 1 is the mean change from baseline in CDASI activity score at Week 12. The placebo-adjusted treatment effect is defined as the difference (mean change from baseline at Week 12 in the active treatment group minus the mean change from baseline at Week 12 in the placebo group) in the mean change of CDASI activity score from baseline at Week 12. A successful treatment should *decrease* CDASI activity score and therefore the

desired treatment effect is negative. The value -5 is viewed as the minimal clinically relevant value of the treatment effect.

The treatment is declared efficacious if each of the following conditions is satisfied:

- C1: Estimated value of the treatment effect is lower than -5.
- C2: An upper limit of 2-sided 90% confidence interval for the treatment effect is below zero.

5.1.2. Hypotheses and Decision Rules in Stage 2 and Amended Stage 2

The primary endpoint for Stage 2 and Amended Stage 2 is the change from baseline in CDASI activity score at Week 12 and uses data from Stage 1, Stage 2, and Amended Stage 2. No p-values will be presented for the comparisons listed in the objectives and endpoints of this pooled analysis. The placebo-adjusted treatment effect is defined as the difference (mean change from baseline at Week 12 in the active treatment group minus the mean change from baseline at Week 12 in the placebo group) in the mean change of CDASI activity score from baseline at Week 12. No hypotheses will be tested in the pooled analysis.

5.1.3. Hypotheses and Decision Rules in Stage 3

The primary endpoint in Stage 3 is safety, including incidence of adverse events (AEs) laboratory abnormalities, changes in vital signs, and electrocardiogram (ECG) findings. Major efficacy endpoints, including the TIS, the components of the TIS, and the CDASI activity and damage scores, are assessed as secondary endpoints. No hypotheses will be tested in Stage 3.

5.2. General Methods

Pfizer's standards will be used to describe distributions of outcomes for each of the visits and treatment groups in each stage. In addition to that the following statistical methods will be used. To explore the data further and to assess the goodness-of-fit of all statistical models, separate SAS datasets and common separated value files will be provided by the clinical programmer to the statistician.

5.2.1. Analyses for Continuous Longitudinal Data

5.2.1.1. Longitudinal Analysis of Covariance (LANCOVA) Model

A discussion of this model may be found in Lu (2010). We will use the following variations of the method: LANCOVA-P and LANCOVA-S where letters P and S denote the versions that are used for primary (P) and sensitivity (S) analyses.

The LANCOVA-P model uses the change from baseline as an outcome and the baseline value as a covariate. The model assumes visit-independent adjustment of the mean outcome for baseline, saturated treatment by time model for the mean and an un-structured within subject error covariance matrix. Treatment and time are considered as factor variables and treatment by time is considered as unstructured interaction effect.

The LANCOVA-S model also uses the change from baseline as an outcome and the baseline value as a covariate. The model assumes a saturated baseline by time and treatment by time fixed effects and an un-structured within subject error covariance. Treatment and time are considered as factor variables and baseline by time and treatment by time are considered as unstructured interaction effects. This allows the baseline and treatment effects to vary over time.

Variations of LANCOVA-P and LANCOVA-S models with the covariance matrices that have less general structure (eg, compound symmetry) may be considered if there are convergence issues with the primary versions of the model.

The analysis will provide an estimate and a two-sided 90% confidence interval for the difference (for each of the active doses against placebo) in the expected values of the outcome at multiple visits.

The sample SAS code for the LANCOVA calculations is presented in Section 9.6.

5.2.1.2. Conventional ANCOVA Model

The conventional ANCOVA method will use the difference between post-baseline and baseline values as an outcome and the baseline value as a covariate and will provide an estimate and a two sided 90% confidence interval for the difference (each of the active doses against placebo) in the expected values of the outcome at each of the individual visits.

The ANCOVA-based estimate of the treatment effect at the particular visit incorporates only a visit-specific post-baseline observations of outcome while the LANCOVA-based estimate simultaneously estimates treatment effect at all treatment visits using all of the observed data. The ANCOVA-based estimate will be used for sensitivity analysis. A qualitative similarity of the LANCOVA and ANCOVA-based estimates of the treatment effect will support the robustness of the primary (LANCOVA-based) estimate.

The sample SAS code for the ANCOVA calculations is presented in Section 9.6.

5.3. Methods to Manage Missing Data

• In the longitudinal modeling (LANCOVA) of repeated measures of continuous outcomes (both efficacy measures and covariates) it is assumed that missing data are generated by the "missing at random" mechanism and, therefore imputation of the missing data is not necessary.

• For other endpoints, statistical analyses will be based on available data. Missing data will not be imputed.

6. ANALYSES AND SUMMARIES

6.1. Analyses and Summaries During Stage 1

6.1.1. Primary Endpoint in Stage 1

The primary endpoint is the change from baseline in CDASI activity score at Week 12.

6.1.1.1. Primary Analysis in Stage 1

- Analysis time point: Week 12.
- Analysis population: subset of FAS1 that *includes baseline observations and observations collected at weeks 1-12*. Note that subjects with some missing data are included.
- Analysis methodology: change from baseline will be analyzed using the LANCOVA-P model (as described in Section 5.2.1.1).
- Supporting objective: Primary Objective.
- Reporting results (for CDASI activity score change from baseline at Week 12):
 - The sample size, mean, standard deviation, median, minimum and maximum will be presented for each treatment arm.
 - The LS means, 90% confidence interval for the LS means, difference between the LS means of treatment groups (active-placebo) and the corresponding 90% confidence interval for the estimate. These summary statistics will also be reported for the percent change from baseline in CDASI activity score at Week 12.

6.1.1.2. Sensitivity Analyses 1-3 in Stage 1

• The sensitivity analyses will explore sensitivity of the result of the primary analysis to the following variatons of the data analysis methods (as described in Section 5.2.1) and data sets (as described in Sections 4.1.1, 4.2.1).

Table 2.	Details of Approaches to	Sensitivity Analyses of Primary	Analysis

Sensitivity Analysis	Data Set (population)	Included Observations (Time Window)	Method
1	FAS1	Baseline, weeks 1-12	LANCOVA-S
2	FAS1	Baseline, week 12	ANCOVA
3	PPAS1	Baseline, weeks 1-12	LANCOVA-S

- Here FAS1 and PPAS1 denote full and per-protocol data sets defined in Sections 4.1.1 and 4.2.1. The reporting results will include the LS means, 90% confidence interval for the LS means, difference between the LS means of treatment groups (active-placebo) and the corresponding 90% confidence interval.
- Note that in the sensitivity analyses (similarly to the primary analysis) we *do not use* data collected after Week 12 visit.
- In addition, the analysis for the CDASI-A in Section 6.1.1.1 may be repeated adjusting for subjects meeting protocol discontinuation criteria for use of prohibited medications as an intercurrent event (if any). Data from visits occurring after meeting discontinuation criteria for use of prohibited medications will be censored from this analysis.

6.1.2. Secondary Endpoint(s) in Stage 1

• Absolute values and change from baseline of CDASI activity and CDASI damage scores at all scheduled time points.

In the analyses (both the secondary analysis and corresponding sensitivity analyses) the observations collected after Week 12 are included into the modeling. The main goal of the analyses is to produce the estimate and two-sided confidence interval (with 90% coverage) of the treatment effect at all scheduled time points (ie, 1, 4, 8, 12, 16, 20, 24, 28 weeks). In addition to that the standard descriptive statistics for each of the two outcomes (CDASI activity and CDASI damage score), each of the treatment groups and each visit will be presented for absolute values of the scores. The descriptive statistics will include number of observations, mean, standard deviation, median, minimum and maximum values.

6.1.2.1. Analysis of Secondary Endpoints in Stage 1

- Analysis time points: 1, 4, 8, 12, 16, 20, 24, 28 weeks.
- Analysis population: FAS1.
- Analysis methodology: change from baseline will be analyzed using the LANCOVA-P model (as described in Section 5.2.1.1).
- Supporting objective: Secondary Objective.
- Reporting results (for CDASI scores changes at each visit):

- The sample size, mean, standard deviation, median, minimum and maximum will be presented for each treatment arm.
- The LS means, 90% confidence interval for the LS means, difference between the LS means of treatment groups (active-placebo) and the corresponding 90% confidence interval for the estimate. Plots of this data will also be presented.

6.1.2.2. Sensitivity Analyses 1-3 in Stage 1

• The analyses will explore sensitivity of the result of the primary analysis to the following variatons of the data analysis methods (as described in Section 5.2.1) and data sets (as described in Sections 4.1.1, 4.2.1).

 Table 3.
 Details of Approaches to Sensitivity Analyses of Secondary Analysis

Sensitivity Analysis	Data Set (population)	Included Observations	Method
1	FAS1	All	LANCOVA-S
2	FAS1	All	ANCOVA
3	PPAS1	All	LANCOVA-S

• Here FAS1 and PPAS1 denote full and per-protocol data sets defined in Sections 4.1.1 and 4.2.1. The reporting results will include the LS means, 90% confidence interval for the LS means, difference between the LS means of treatment groups (active-placebo) and the corresponding 90% confidence interval.

6.1.3.3. Additional Biomarkers (Gene Signature Panel in Blood and Tissue, Muscle Bone and Blood Biomarkers, Autoantibody Concentrations in Serum/Plasma) in Stage 1

These analyses will be reported in the additional exploratory analysis report.

6.1.3.4. Patient Reported Outcomes (SF36, DLQI, 5D Itch Scale) and Physician's Evaluation of Disease (PhGA), CDASI Activity and CDASI Damage Subscores in Stage 1

- Analysis population: FAS1.
- Analysis time points: all visits with samples taken.
- Analysis methodology: summary statistics. For SF36(PCS and MCS scores), DLQI,
 5D itch scale and PhGA scores the change from baseline will be also investigated by applying the LANCOVA-P model (as described in Section 5.2.1.1).
- Supporting objective: Exploratory Objective.
- Reporting results:
 - Change from baseline: The sample size, mean, standard deviation, median, minimum and maximum by visit.
 - Absolute values: The sample size, mean, standard deviation, median, minimum and maximum by visit.
- For the SF36 (short form Health Survey) observations two summary component scores (PCS and MCS) and 8 scale subscores (PF, RP, BP, GH, VT, SF, RE, and MH) will be summarized.

- For the DLQI (Dermatology and Life Quality Index), 5D Itch Scale and physician's evaluation of disease (PhGA) scores a single score summarizes each of the corresponding patient-reported outcomes.
- For the CDASI activity score we will analyze the following subscores: total extent score (ES), total erythema score (ER), total scaling (SC) and total erosion/ulceration scores (EU), Gottorn hands score (GHS), peringual score (PS), and alopecia score (AS).
- For the damage score we will analyze the following subscores: total poilkiloderma score (POLS), total calcinosis score (CALS) and Gotorn's hands damage score (GHDS).

We emphasize that the LANCOVA-P models will only be created for SF36 (PCS and MCS scores), DLQI, 5D itch scale and PhGA scores. Ad-hoc analyses for PROs with minimum clinically important differences may be performed.

6.2. Analyses and Summaries During Stage 2 and Amended Stage 2

6.2.1. Primary Endpoint in Stage 2 and Amended Stage 2

The primary endpoint is the change from baseline in CDASI activity score at Week 12.

6.2.1.1. Primary Analysis in Stage 2 and Amended Stage 2

The treatment effect is defined as the difference (between each pooled active treatment group and the pooled placebo group across Stage 1, Stage 2, and Amended Stage 2 in the mean change of CDASI activity score from baseline at Week 12. The pooled 600 mg treatment arm will include data from baseline to Week 12 from participants assigned to the 600 mg in Stage 1, the 600 mg arm in Stage 2, and the 600 mg -> placebo arm in Amended Stage 2. The pooled 150 mg treatment arm will include data from baseline to Week 12 from participants assigned to the 150 mg arm in Stage 2 or the 150 mg -> placebo arm in Amended Stage 2. The pooled placebo arm will include data from baseline to Week 12 from participants assigned to the placebo arm in Stage 1, the placebo arm in Stage 2, the placebo ->150 mg arm in Amended Stage 2, and the placebo ->600 mg arm in Amended Stage 2.

- Analysis time point: Week 12.
- Analysis population: subset of FAS2 that includes baseline observations and observations collected at weeks 1-12 for subjects in Stage 1, Stage 2, and Amended Stage 2. Note that subjects with missing data are included.
- Analysis methodology: change from baseline will be analyzed using the LANCOVA-P model (as described in Section 5.2.1.1).
- Supporting objective: Primary Objective.

- Reporting results [for CDASI activity score change (between each active treatment group and placebo group across Stage 1, Stage 2, and Amended Stage 2) from baseline at Week 12]:
 - The sample size, mean, standard deviation, median, minimum and maximum will be presented for each treatment arm. Results will also be presented by study stage for these summary statistics.
 - The LS means, 90% confidence interval for the LS means, difference between the LS means of treatment groups (each active treatment arm placebo across the two stages) and the corresponding 90% confidence interval for the estimate. No p-values will be computed for the analysis in this stage.

6.2.1.2. Secondary Analysis in Stage 2 and Amended Stage 2

Data permitting, the secondary analysis for the primary endpoint in Stage 2 will be the PF-06823859 exposure-response analysis of the combined data from Stage 1, Stage 2, and Amended Stage 2. The Population Modeling Analysis Plan will describe the evaluation of the relationship between PF-06823859 exposures and response at Week 12.

6.2.1.3. Sensitivity Analyses in Stage 2 and Amended Stage 2

The sensitivity analyses from Stage 1 (Section 6.1.1.2) may be repeated using the pooled data from Stage 1, Stage 2, and Amended Stage 2 using the PFASS. For these sensitivity analyses, estimates and CIs may be produced. No p-values will be produced.

The analysis for the CDASI-A in Section 6.2.1.1 using PFASS may be repeated adjusting for subjects meeting protocol discontinuation criteria for use of prohibited medications as an intercurrent event (if any). Data from visits occurring after meeting discontinuation criteria for use of prohibited medications will be censored from this analysis.

6.2.1.4. Supportive Analyses in Stage 2 and Amended Stage 2

Supportive analyses may be reported in Stage 2. For one supportive analysis, summary statistics will be reported by treatment sequence and visit for the participants in the FASA2 from baseline to Week 28. The sample size, mean, standard deviation, median, minimum and maximum will be presented.

6.2.2. Secondary Endpoint(s) in Stage 2 and Amended Stage 2

The analyses and summaries of the secondary endpoints in Stage 2 will be the same as those in Stage 1 (Section 6.1.2) except that they will be conducted for the data across Stage 1, Stage 2, and Amended Stage 2 and use the appropriate Stage 2 analysis set. No p-values will be presented for these analyses.

6.2.3. Exploratory Efficacy Endpoints in Stage 2, and Amended Stage 2

The analyses and summaries of the exploratory efficacy endpoints in Stage 2 will be the same as those in Stage 1 (Section 6.1.3) except that they will be conducted for the data across Stage 1, Stage 2, and Amended Stage 2 and use the appropriate Stage 2 analysis set.

Statistical summaries will stratified by treatment group. No p-values will be presented for these analyses.

Percent change from baseline in the CDASI activity score will also be analyzed and reported in the same manner as the change from baseline CDASI activity score as described in Section 6.2.1.1.

For PROs newly added to Amended Stage 2 that were not collected in Stage 2, including the PtGA, HAQ-DI, CCI and EQ-5D-5L & EQ-VAS, descriptive statistics will be provided at each visit using the FASA2 and reported by treatment group. The reporting results for these PROs will be the same as those in Section 6.1.3.4, with some additional details provided below:

- For the PtGA and EQ-VAS scores, a single score summarizes each of the corresponding patient-reported outcomes (see Sections 9.4.5 and 9.4.8).
- For the CCl each of the three questions will be summarized by a single score (see Section 9.4.7).
- For the EQ-5D-5L, the summed number of checked boxes under each of the five sections will be reported (see Section 9.4.8).
- For the HAQ-DI, a single averaged score summarizes each of the corresponding patient-reported outcomes under the eight sections (see Section 9.4.6). In sections of the HAQ-DI relating to aids or devices or help from another person, each checkable box will be treated as binary data and summarized with proportions and frequency counts. A single score summarizes the severity of pain VAS.

6.3. Analyses and Summaries During Stage 3

6.3.1. Primary Endpoint in Stage 3

The primary endpoint in Stage 3 includes the incidence of adverse events (AEs) laboratory abnormalities, changes in vital signs, and electrocardiogram (ECG) findings. All safety summaries and analyses will be performed as specified in Section 6.7.

6.3.2. Secondary Endpoint(s) in Stage 3

6.3.2.1. Total Improvement Score in Stage 3

- Analysis population: FAS3.
- Analysis time points: Week 12 and intermediate scheduled time points.
- Analysis methodology: The TIS at post baseline visits are scored relative to baseline and the TIS at baseline is 0 by definition; thus all analyses are performed directly on the TIS. The estimates of the treatment effect from baseline to Week 12 will be obtained by MMRM where the TIS will be used as a dependent variable. This model uses fixed effects for treatment, time (visit), treatment by time, and a random effect for subject, Due to the unknown nature of the longitudinal data, different covariance

structures among repeated measures will be examined based on model diagnostics starting with the unstructured variance-covariance model.

- Supporting objective: Secondary objective.
- Reporting results: The absolute value of the TIS at each post baseline visit will be summarized by the following descriptive statistics:
 - The sample size, mean, standard deviation, median, minimum and maximum will be presented for each treatment arm (active and placebo).
 - The LS means, 90% confidence interval for the LS means, difference between the LS means of treatment groups (active treatment arm placebo) and the corresponding 90% confidence interval for the estimate. Plots of this data will also be presented. No p-values will be computed for the analysis in this stage.
 - The proportion of subjects achieving minimal, moderate, and major responses in their TIS score (defined as scores of ≥20, ≥40, and ≥60 in the TIS respectively) will also be reported by treatment.

6.3.2.1.1. Supportive and Sensitivity Analyses for the TIS in Stage 3

Additional analyses may be performed for the TIS in Stage 3.

- Summary statistics will be reported by treatment sequence and time for the participants in the FAS3 from baseline to Week 24. The sample size, mean, standard deviation, median, minimum and maximum will be presented.
- The analysis for the TIS in Section 6.3.2.1 may be repeated adjusting for subjects meeting protocol discontinuation criteria for use of prohibited medications as an intercurrent event (if any). Data from visits occurring after meeting discontinuation criteria for use of prohibited medications will be censored from this analysis.
- The analysis for the TIS in Section 6.3.2.1 may be repeated using treatment sequence as a covariate from baseline to Week 24.
- The analysis for the TIS in Section 6.3.2.1 may be repeated using last observation carried forward (LOCF) for missing TIS values.

6.3.2.2. Components of the TIS in Stage 3

The absolute values and change from baseline in each of the components of the TIS, including the PhGA (from the MDAAT), PtGA, MMT, HAQ-DI, muscle enzymes, and extramuscular global assessment, will be summarized by descriptive statistics at each visit, including number of observations, mean, standard deviation, median, minimum and maximum values.

Estimates of treatment effect for selected components of the TIS (PhGA, PtGA, extramuscular global assessment, HAQ-DI, and MMT-8) will be obtained by LANCOVA in the same manner as described in Section 6.1.2 where the change from baseline of a specified component will be used as a dependent variable. The absolute values of these five components will also be assessed using an MMRM model. Estimates and the confidence intervals for treatment effect will be presented for each of these methods. Accompanying plots may also be provided.

6.3.2.3. CDASI Activity and CDASI Damage Scores in Stage 3

The absolute values and change from baseline of CDASI activity and damage scores at all scheduled time points will be summarized by descriptive statistics, including number of observations, mean, standard deviation, median, minimum and maximum values.

